5.7.2. Analysis of Secondary Efficacy Variables

All secondary efficacy variables will be analyzed based on the mITT using the same MMRM as described in [Section 5.7.1](#) to compare fasinumab doses with placebo without multiplicity adjustment. These models will include fixed effect terms for randomization strata, corresponding baseline value, treatment, visit, and treatment-by-visit interaction. LS mean with standard errors, LS mean difference with standard error, and its 95 % confidence interval will be provided. The graph of LS-mean +/- SE by visit will be provided. In addition, for each secondary variable, absolute value and change from baseline value will be summarized and graphed by visit.

5.7.3. Analysis of Exploratory Variables

Responder analyses

The percentage of patients who are responders based on the variables listed in [Section 4.5.3](#) are defined by 30% reduction and 50% reduction from baseline to week 16 will be summarized by the treatment group. These response-based categorical exploratory variables will be analyzed for FAS using the Cochran-Mantel-Haenszel (CMH) test, stratified by the randomization strata.

Cumulative distribution of percent change from baseline in average daily LBPI score and RMDQ total score will be presented by treatment group. The cumulative distribution plot displays a continuous plot of the percent change from baseline on the X-axis and the percent of patients experiencing that change on the Y-axis. Different responder definitions can be identified along the cumulative distribution curve.

Continuous endpoints

All continuous exploratory variables will be analyzed for FAS using the same MMRM as described in [Section 5.7.1](#) to compare fasinumab doses with placebo without multiplicity adjustment. These models will include fixed effect terms for randomization strata, corresponding baseline value, treatment, visit, and treatment-by-visit interaction. LS mean with standard errors, LS mean difference with standard error, and its 95 % confidence interval will be provided. The graph of LS-mean +/- SE by visit will be provided. In addition, each variable, absolute value and change from baseline value will be summarized and graphed by visit.

Rescue Medication

The percentage of patients who use rescue medication between baseline and week 16 will be summarized by the treatment group. The categorical exploratory variable will be analyzed for FAS using the Cochran-Mantel-Haenszel (CMH) test, stratified by the randomization strata.

Number of days patients used rescue medication during the treatment period (Day1 to Week 2, Week 2 to Week 4, Week 4 to Week 8, Week 8 to Week 12, Week 12 to Week 16) will be summarized descriptively by treatment group. Weekly average amount of rescue medication use will be summarized descriptively by treatment group.

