8.3. Exploratory Endpoints

Exploratory endpoints are:

- The change from baseline at week 16 in the percentage of patients who are responders defined by 30% reduction and 50% reduction for:
 - average daily LBPI NRS score
 - RMDQ total score
 - PGA of LBP score
 - Change from baseline at week 16 in the MOS sleep subscale score
 - Change from baseline at week 16 in the SF-36 subscale scores
 - Change from baseline at week 16 in the EQ-5D-5L
 - Change from baseline at week 16 in the percentage of patients who use rescue medication for LBP

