1.1.4. Other Objectives

Exploratory objectives of the study are:

- To evaluate the efficacy of fasinumab compared to placebo, as measured by the percentage of patients who are responders defined by 30% reduction and 50% reduction from baseline to week 16 for:
 - Average daily LBPI NRS score
 - RMDQ total score
 - PGA of LBP score
- To evaluate the efficacy of fasinumab compared to placebo, as measured by the change from baseline to week 16 in the Medical Outcomes Study (MOS) sleep subscale score
- To evaluate the efficacy of fasinumab compared to placebo, as measured by the change from baseline to week 16 in the Short Form (36) Health Survey (SF-36) subscale scores
- To evaluate the efficacy of fasinumab compared to placebo, as measured by the change from baseline to week 16 in the EuroQol 5 Dimensions 5 Levels Questionnaire (EQ-5D-5L)
- To evaluate the efficacy of fasinumab compared to placebo, as measured by the percentage of patients who use rescue medication for LBP at week 16
- To characterize the PK profile of fasinumab

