4.4.3. Exploratory Variable(s)

Exploratory endpoints in the study are:

- The percentage of patients who are responders defined by 30% reduction and 50% reduction from baseline to week 16 in:
 - Average daily LBPI NRS score
 - RMDQ total score
 - PGA of LBP score
- Cumulative distribution of percent change from Baseline in average LBPI score to Week 16
- Cumulative distribution of percent change from Baseline in RMDQ total score to Week 16
- Change from baseline to weeks 2, 4, 8, 12 and 16 in the MOS-Sleep subscale score
- Change from baseline to weeks 2, 4, 8, 12 and 16 in the SF-36 subscale scores
- Change from baseline to weeks 2, 4, 8, 12 and 16 in the EQ-5D-5L visual analogue scale (VAS) and utility index scores
- Usage of rescue medication (percentage of patients who use rescue medication for LBP, number of days of usage, and weekly average amount taken during weeks 2, 4, 8 12, and 16)

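### The rescue-medication objective is set at week 16, but the only planned test is on use over the whole interval from baseline to week 16, and no week-16 percentage is planned

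*SAP*

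**What the plan says.** The objective has a time point. SAP 1.1.4 evaluates efficacy "as measured by the percentage of patients who use rescue medication for LBP at week 16", and protocol 2.4 sets the same objective at the same week.

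The endpoint wordings vary:
- Protocol 8.3 keeps week 16 but makes it a change: "Change from baseline at week 16 in the percentage of patients who use rescue medication for LBP".
- SAP 4.4.3 lists the percentage of users, followed by "number of days of usage, and weekly average amount taken during weeks 2, 4, 8 12, and 16".

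The analysis is in SAP 5.7.3 under Rescue Medication: "The percentage of patients who use rescue medication between baseline and week 16 will be summarized by the treatment group". The next sentence supplies the test: "The categorical exploratory variable will be analyzed for FAS using the Cochran-Mantel-Haenszel (CMH) test, stratified by the randomization strata". The remaining rescue output is days of use by interval, ending "Week 8 to Week 12, Week 12 to Week 16) will be summarized descriptively by treatment group", and the weekly average amount, also descriptive.

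SAP 1.1.5, the section for modifications from the protocol's statistical section, states only which protocol amendment the SAP is based on. It lists no modification.

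**The concern.** A yes/no variable over an interval of about 16 weeks is a different quantity from a yes/no variable at week 16. If the interval variable means at least one use, it never reverts. A patient who takes rescue medication in the first days and none afterwards counts as a user, just like a patient still taking it at week 16. Early use is plausible, because NSAIDs and opioids are stopped at the pre-randomization visit (protocol 5.7.2) and paracetamol/acetaminophen is the only rescue allowed for low back pain (protocol 5.2).

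At stake is how the rescue result is read. Readers use it to judge whether a pain score at week 16 was reached with more or less background analgesia. A p-value for use at any time since baseline does not address that, and could be reported under an objective that names week 16.

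**Working it through.** **Step 1. Set the passages side by side.**

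| Place | Quantity | Time point | Test |
|---|---|---|---|
| Protocol 2.4, SAP 1.1.4 (objective) | % of patients using rescue | week 16 | not stated |
| Protocol 8.3 (endpoint) | change from baseline in that % | week 16 | not stated |
| SAP 4.4.3 (variable) | % using, days used, weekly amount | weeks 2, 4, 8, 12, 16, at least for the amount | not stated |
| SAP 5.7.3 (analysis) | % using | baseline to week 16 | stratified CMH, FAS |
| SAP 5.7.3 (analysis) | days used | by interval, including week 12 to 16 | none |
| SAP 5.7.3 (analysis) | weekly average amount | weekly | none |

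No row of SAP 5.7.3 holds a percentage at week 16. The mismatch rests on the text alone. The documents give no figure for this endpoint to reproduce.

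**Step 2. How far apart can the two variables be?** This needs assumed rates, so it is illustration only.

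Inputs: 563 patients randomized at the clinical hold (SAP 1, Overview), so 563/4 = 140.75, about 141 per arm; 16 × 7 = 112 days. Assumed: each patient has a daily use probability p following a beta distribution with mean m = 0.30 in one arm and 0.20 in the other, and parameter total c = 1, 2 or 5 (larger c means more alike patients).

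P(any use in k days) = 1 − E[(1−p)^k] = 1 − B(a, b+k)/B(a, b), with a = mc and b = (1−m)c. Power is for a two-sided 0.05 two-proportion comparison.

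| c | Any use, 112 days | Power | Any use, 7 days | Power |
|---|---|---|---|---|
| 1 | 81.3% vs 66.6% | 81% | 57.7% vs 42.5% | 73% |
| 2 | 93.4% vs 83.1% | 77% | 68.1% vs 52.0% | 79% |
| 5 | 99.4% vs 96.6% | 40% | 79.5% vs 63.6% | 84% |

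The percentages and treatment differences change substantially. Power moves in either direction.

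**Step 3. Sensitivity to dropout.** Take m = 0.30 and let 25% of an arm withdraw at day 28.
- Interval use, c = 5: use by day 28 is 96.0%, so 0.75 × 99.4% + 0.25 × 96.0% = 98.6%, a fall of 0.8 points.
- Seven-day week-16 use with dropouts counted as non-users, c = 5: 0.75 × 79.5% = 59.6%, a fall of 19.9 points.
- At c = 1 the falls are 2.4 and 14.4 points.

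The week-16 variable is the more fragile of the two unless missing data are handled explicitly.

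**Step 4. Which diary days are usable at week 16?** SAP 4.4.1 says the week-16 pain average has 6 diary days, because the visit-day entry was not captured. Protocol 3.1 and 5.2.1 prohibit rescue for 48 hours before a scheduled visit. That leaves about 6 − 2 = 4 days on which use is allowed. The pain-average window is therefore a poor default for rescue use, since part of it measures compliance with the prohibition. Under the same assumptions with c = 5, a 4-day window gives 66% vs 50% and power 81%.

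**The case against.** The strongest reply is that this is loose drafting in an exploratory endpoint. SAP 5.7.3 never says any use or at least one use. SAP 4.4.3 can be read so that the listed weeks attach only to the amount ("weekly average amount taken during weeks 2, 4, 8 12, and 16"), leaving the percentage with no time point. Protocol 8.3 words the endpoint differently again, so the SAP may be a rough paraphrase of it. Late rescue use is not invisible either, since days of use from week 12 to week 16 and weekly amounts are shown by arm.

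Much of this stands. At least one use is an inference, though the SAP offers no other definition. SAP 4.4.3 does not settle the time point of the percentage, and the descriptive output does inform on late use. None of it supplies the percentage named in the objective.

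A reader might also infer two stronger things that the documents do not support. One is that the interval variable costs power. No rescue rate is given, and under assumed rates it has more power in one of the three cases in Step 2 and less in the other two. The other is that the interval variable favours the arm with more dropout. Withdrawal by arm is not in the documents. Patients stopping drug are asked to continue visits (protocol 5.3.2, 6.2.7), and after the hold they were to be encouraged to stay to week 36 (SAP 1). In the assumed model, week-16 use is also the more affected when dropouts count as non-users.

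**Conclusion.** The concern holds as a mismatch between objective and analysis. The quantity tested is not the one named in the exploratory objective, the named quantity is not planned even descriptively, and the change is not declared. This rests on the text and on reading the interval variable as at least one use.

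Its numerical size cannot be given from the documents; the illustration shows only that the two variables can differ widely. Severity is minor. The endpoint is exploratory and tested without multiplicity control, and the primary conclusions do not depend on it.

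**What to change.** Before database lock, revise SAP 5.7.3 as follows:

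1. Define a week-16 yes/no variable: any EDiary rescue use in a stated window ending at or shortly before week 16, with enough days outside the 48-hour pre-visit period. Candidates are the week 12 to week 16 interval that 5.7.3 already uses, or the last 7 diary days before the 48-hour period.
2. State how missing week-16 diaries and withdrawals are handled, for example by multiple imputation with a sensitivity analysis counting such patients as users.
3. Apply the stratified CMH test to this variable, and summarize the same percentage at weeks 2, 4, 8 and 12.
4. Keep use between baseline and week 16 as a descriptive summary, defined explicitly as at least one use if that is meant.
5. Reconcile protocol 2.4 and 8.3 with SAP 1.1.4, 4.4.3 and 5.7.3, including the change-from-baseline wording.

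If the sponsor prefers interval use as the tested variable, the alternative is to amend the objective and declare the change in SAP 1.1.5.

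The cost is SAP wording and a little programming, since daily use is already recorded through the week 16 visit (protocol 6.1, Table 1 notes). The drawback is that a week-16 variable is more sensitive to missing data than interval use, which is why item 2 is needed.

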5.8. Analysis of Safety Data

The analysis of safety and tolerability will be performed on the SAF, as defined in [Section 3.3](#). The safety analysis will be based on the reported AEs and other safety information (clinical

laboratory evaluations, vital signs, physical exam and 12-lead ECG). Thresholds for Potential Clinically Significant Values (PCSV) in laboratory variables, vital signs and ECG are defined in [Appendix 10.2](#).

The summary of safety results will be presented for each treatment group.

Period of observation: The observation period will be divided into three segments: pre-treatment, on-treatment, and follow-up period.

- The pre-treatment period is defined as the time from signing the ICF to before the first dose of study drug.
- The on-treatment period is defined as the day from first dose of study drug to 4 weeks after the last dose of SC study drug or 8 weeks after the last dose of IV study drug, whichever is later.
- The Post/Treatment follow-up period is defined as from the end of the on-treatment period+1 day to the end of study visit (week 36).

Unless otherwise noted, summaries of safety variables will use data from the on-treatment period. Listings of safety variables will include data from all periods and values occurring during the pre-treatment and follow-up period will be flagged in the listings.

Day 1 is the first day of investigational product, Day –1 is the day before, and there is no Day 0.

The time interval to detect any on-treatment event or abnormality is the on-treatment period. Data collected outside this interval will be excluded from the estimation of descriptive statistics and identification of abnormalities for laboratory evaluations, ECGs and vital signs. All post-baseline data during the interval will be using in the PCSV analysis including scheduled and unscheduled assessments.

5.8.1. Adverse Events

The verbatim text, the PT, and the primary SOC will be listed in patient listings. Summaries that include frequencies and proportions of patients reporting AEs will include the PTs and the SOCs.

Pre-treatment AEs are defined as AEs that developed or worsened during the pre-treatment period.

Treatment-emergent AEs (TEAEs) are defined as AEs that developed or worsened during the on-treatment period.

Post-treatment AEs are defined as AEs that developed or worsened more than 28 days after the last SC dose of investigational product or 56 days after the last IV dose of investigational product.

The focus of adverse event reporting in the clinical study report will be on TEAEs. Post-treatment AEs and AEs during the combined study periods will also be summarized.

For details on handling missing data and partial dates, see [Section 6](#).

Summaries of all TEAEs in each treatment group will include:

- Overview of TEAEs, summarizing number of events, summarizing number and percentage of patients with any
 - Total number of TEAEs
 - Total number of Serious TEAEs
 - Patients with any TEAEs
 - Patients with Serious TEAEs
 - Patients with TEAE leading to permanent treatment discontinuation
 - Patients with TEAE leading to withdrawal from study
 - Patients with TEAE leading to death
 - Patients with any AESI's
- TEAEs by SOC and PT
- TEAEs by SOC, PT, and severity
- Treatment-related TEAEs by SOC, PT, and severity
- TEAEs Resulting in Permanent Study Drug Discontinuation by SOC and PT
- AESI by SOC and PT
- Post-Treatment TEAEs by SOC and PT
- Post-Treatment TEAEs by SOC, PT, and severity
- All On-Treatment and Post-Treatment AEs by SOC and PT
- All On-Treatment and Post-Treatment AEs by SOC, PT, and severity
- Serious TEAEs by SOC and PT
- Non-serious TEAEs by SOC and PT
- Post-treatment Serious AEs by SOC and PT
- All Serious AEs by SOC and PT
- Listing of Patients with Serious TEAEs
- Listing of Patients with AESIs
- Listing of deaths
- Listing of AEs leading to death

Counts will be provided by treatment group for each PT within each SOC. Percentages will be calculated using the number of patients from the SAF in each treatment group.

Primary SOC's will be sorted by decreasing frequency of investigational product, with the total overall classes coming first and labeled "Any class". Within each primary SOC, PTs will be sorted by decreasing frequency of investigational product. For tables presenting severity of events, the worst severity will be chosen for patients with multiple instances of the same event.

A second type of table with counts of each primary SOC in decreasing order of frequency will be provided. A third type of table with counts of each PT in decreasing order of frequency will also be provided.

Common TEAEs (preferred terms $\geq 5\%$ in any treatment group) will be summarized in the report.

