Patients will be instructed to stop using all prohibited medications at the pre-randomization visit. Patients will receive paracetamol/acetaminophen to be used as study-provided rescue medication. In the event of inadequate LBP relief, paracetamol/acetaminophen may be taken as needed, according to local standard of care, to a maximum total dose of 2600 mg (325 mg x 8) per day in North America and 2500 mg (500 mg x 5) per day in Europe, starting at the pre-randomization visit through week 16.

Patients must have a mean daily LBPI NRS score ≥ 4 during the pre-randomization period, in order to be eligible for study participation. Patients may not use paracetamol/acetaminophen for 48 hours prior to the start of a scheduled study visit or during a study visit, in order to minimize the confounding effects of rescue medication on efficacy measures.

Confirmation that there are no exclusionary findings on lumbar MRIs, any hip or knee MRI of joints with a K-L score ≥ 3 , or any other joint on which an MRI was performed during screening must be received before a patient can be randomized.

- **Treatment Period (day 1 through week 16):** The treatment period will begin at the randomization visit (baseline/day 1) and continue through the week 16 visit. Patients who meet study entry criteria will be randomized and will undergo baseline assessments at the day 1 visit. For patients randomized to SC administration, a loading dose equivalent to 2 times the maintenance dose will be administered on day 1.

Patients randomized to 6 mg or 9 mg fasinumab SC Q4W and placebo IV 9 mg Q8W will receive 2 SC injections of fasinumab on day 1 (SC loading dose), 1 SC injection at weeks 4, 8, and 12, and 1 IV infusion of matching placebo on day 1 and at week 8.

Patients randomized to 9 mg fasinumab IV Q8W and placebo SC Q4W will receive 1 IV infusion of fasinumab on day 1 and at week 8, 2 SC injections of matching placebo on day 1 (placebo for SC loading dose) and 1 SC injection of matching placebo at weeks 4, 8, and 12.

Patients randomized to placebo SC Q4W and placebo 9 mg IV Q8W will receive 2 SC injections of matching placebo to fasinumab on day 1 (SC loading dose), 1 SC injection of matching placebo at weeks 4, 8, and 12, and 1 IV infusion of matching placebo on day 1 and at week 8.

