5. STUDY TREATMENTS

5.1. Investigational Treatment

Patients will be randomized to 1 of the following 4 treatment groups:

1. Fasinumab 6 mg SC Q4W and placebo 9 mg IV Q8W
2. Fasinumab 9 mg SC Q4W and placebo 9 mg IV Q8W
3. Fasinumab 9 mg IV Q8W and placebo SC Q4W
4. Placebo SC Q4W and placebo 9 mg IV Q8W

Patients randomized to treatment groups 1 or 2 (6 mg or 9 mg fasinumab) will receive SC injections of fasinumab on day 1, and at weeks 4, 8, and 12 for a total of 4 doses. These patients will also receive matching placebo IV on day 1 and at week 8. For patients randomized to SC administration, a loading dose equivalent to 2 times the maintenance dose will be administered SC on day 1.

Patients randomized to treatment groups 3 or 4 will receive matching placebo to fasinumab SC, including the loading dose on day 1.

Patients randomized to treatment group 3 will receive IV infusions of fasinumab (9 mg) on day 1 and week 8 for a total of 2 doses. Patients randomized to treatment groups 1, 2, or 4 will receive matching placebo to fasinumab IV.

Study drug (fasinumab or placebo) will be administered at the study site after all study visit procedures have been completed. All SC injections will be in the abdomen or thigh. At the day 1 and week 8 visits, patients will receive the SC injection first, followed by the IV infusion. After IV administration of study drug, patients will be observed in the clinic for approximately 2 hours for evidence of a hypersensitivity reaction, and for 1 hour after SC dosing. Instructions for study drug administration are provided in the pharmacy manual. Doses of study drug must be given within ± 7 days from the scheduled dose date. If the window is missed, the dose should not be administered. The next dose should be administered at the next scheduled dosing date.

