9.5.3. Safety Analysis

9.5.3.1. Adverse Events

Definitions

For safety variables, the following observation periods are defined:

- The pretreatment period is defined as the time from signing the ICF to before the first dose of study drug.
- The on-treatment period is defined as the day from first dose of study drug to 4 weeks after the last dose of SC study drug or 8 weeks after the last dose of IV study drug, whichever is later.
- The follow-up period is defined as from the end of the on-treatment period (week 16) to the end of study visit (week 36).

Treatment-emergent adverse events are defined as those that are not present at baseline or that represent the exacerbation of a preexisting condition during the on-treatment period.

Analysis

All AEs reported in this study will be coded using the currently available version of the Medical Dictionary for Regulatory Activities (MedDRA[®]). Coding will be to lowest level terms. The verbatim text, the preferred term (PT), and the primary system organ class (SOC) will be listed.

Summaries of all TEAEs by treatment group will include:

- The number (n) and percentage (%) of patients with at least 1 TEAE by SOC and PT
- TEAEs by severity (according to the grading scale outlined in [Section 7.3.1](#)), presented by SOC and PT
- TEAEs by relationship to treatment (related, not related), presented by SOC and PT

Deaths and other SAEs will be listed and summarized by treatment group.

Treatment-emergent adverse events leading to permanent treatment discontinuation will be listed and summarized by treatment group.

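### SAP 5.8.1 defines post-treatment adverse events with a bare 'or' that conflicts with the later-of rule in SAP 5.8, so as written one event can fall in both classes

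*SAP*

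**What the plan says.** SAP 5.8 divides observation into three segments. The on-treatment segment starts at the first dose and lasts until "4 weeks after the last dose of SC study drug or 8 weeks after the last dose of IV study drug, whichever is later". Follow-up begins one day after that and lasts to the week 36 visit. Protocol 9.5.3.1 has the same later-of rule and places the end of the on-treatment period at week 16.

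SAP 5.8.1 then classifies events. Pre-treatment events are tied to the pre-treatment segment, and treatment-emergent events are "AEs that developed or worsened during the on-treatment period". Post-treatment events are not tied to a segment. They have a rule of their own: onset or worsening "more than 28 days after the last SC dose of investigational product or 56 days after the last IV dose". The later-of qualifier is missing, and the follow-up segment is not mentioned.

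The output list in 5.8.1 asks for post-treatment tables of all AEs and of serious AEs, separate from the treatment-emergent tables. Two of the titles, "Post-Treatment TEAEs by SOC and PT" and its by-severity companion, join the two classes in one name.

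**The concern.** The design is double dummy, so every patient who starts treatment has both a last SC dose and a last IV dose, and therefore two limits. SAP 5.8 closes the on-treatment period at the later limit. Read literally, the *or* in 5.8.1 makes an event post-treatment once it has passed either limit, that is, from the earlier one. Any event between the two limits then satisfies both definitions.

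The content of the post-treatment AE and serious AE tables is at stake. Programmed as written, they would include events that 5.8 assigns to the on-treatment period. The laboratory, vital-sign and ECG summaries in SAP 5.8.4 to 5.8.6 are also split into on-treatment and post-treatment. They would presumably use the 5.8 segments, so the same label could cover different days in the same report.

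This matters more than usual here because the gap between the limits depends on where dosing stopped. According to the SAP Overview, a clinical hold ended dosing before all randomized patients had completed treatment, with 563 randomized at that time.

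**Working it through.** **Inputs**
- End of on-treatment period (SAP 5.8; Protocol 9.5.3.1): later of last SC + 28 days and last IV + 56 days.
- Start of post-treatment AEs, literal SAP 5.8.1: the day after the earlier of the same two limits.
- Schedule (Protocol 3.1): the SC fasinumab arms receive two SC injections on day 1, then "1 SC injection at weeks 4, 8, and 12, and 1 IV infusion of matching placebo on day 1 and at week 8". The IV and placebo arms follow the same visits for both routes. By Protocol Table 1, weeks 4, 8, 12 and 16 are days 29, 57, 85 and 113.
- Dose window (Protocol 5.1): doses "must be given within ± 7 days from the scheduled dose date"; a dose outside its window is skipped and dosing resumes at the next scheduled date.

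**Formulas**
- On-treatment end = max(SC + 28, IV + 56).
- Literal post-treatment start = min(SC + 28, IV + 56) + 1.
- Overlap in days = |(SC + 28) − (IV + 56)|.

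**The plan's own figure.** Full dosing on schedule gives 85 + 28 = 113 and 57 + 56 = 113. Both limits fall on day 113, week 16, as Protocol 9.5.3.1 states.

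**On-schedule dosing patterns**

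| Pattern | Last SC, last IV (day) | SC limit | IV limit | Days in both classes |
|---|---|---|---|---|
| All doses | 85, 57 | 113 | 113 | 0 |
| Stopped after day 1 | 1, 1 | 29 | 57 | 28 (days 30–57) |
| Stopped after week 4 | 29, 1 | 57 | 57 | 0 |
| Stopped after week 8 | 57, 57 | 85 | 113 | 28 (days 86–113) |
| Week-8 IV missed, SC to week 12 | 85, 1 | 113 | 57 | 56 (days 58–113) |

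A day-by-day count of days meeting both definitions gave the same overlaps.

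**Effect of the dose window.** If the week-12 SC dose is *a* days and the week-8 IV dose *b* days off schedule, the limits are 113 + *a* and 113 + *b*, so the overlap is |*a* − *b*|. With each between −7 and +7 it ranges from 0 to 14 days in patients who received every dose. For patients stopped after week 4 the limits are 57 + *a* and 57, so the overlap ranges from 0 to 7 days.

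**Does another reading of the sentence remove the overlap?** Counting only active drug in 5.8.1 does not. An SC-arm patient stopped after day 1 would be post-treatment from day 30, but still on-treatment under 5.8 to day 57 because of the IV placebo dose.

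**After the correction.** If post-treatment events start the day after the later limit, the overlap is 0 in every pattern above.

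**The case against.** The strongest answer is that the parent section already settles the matter. SAP 5.8 sets out three segments that cannot overlap and starts follow-up the day after the on-treatment period ends. Section 5.8.1 sits beneath it and repeats the same limits in days instead of weeks, so its sentence can be read as a shortened form of the 5.8 boundary. On that reading the overlap is zero. The odd table titles can likewise be taken as a slip, since neighbouring outputs refer simply to post-treatment AEs.

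Much of this stands. Double classification arises only if the literal wording of 5.8.1 is programmed in preference to the segments in 5.8. But 5.8.1 does not say that it is abbreviating. Its other two definitions refer to the segments and this one does not. The stated purpose of the SAP is to fix methods before unblinding, so it should not leave a programmer to choose between two boundaries.

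A reader might also infer more than the documents support:
- *That treatment-emergent rates are inflated.* They are not. Those events are defined solely by the on-treatment period, and SAP 5.8.2 restricts the special-interest summaries to treatment-emergent events. Tables combining the two periods need not double count either.
- *That nearly all fully dosed patients are affected.* This depends on how actual dose dates scatter within ±7 days, which is not given. Exactly on schedule, the overlap is zero.
- *That the arms have different windows, or placebo none.* SAP 5.6.2 counts placebo doses of each route as investigational product, and all arms share one schedule. No bias between arms is shown.
- *That a planned comparison of periods is invalidated.* None is planned; summaries are by treatment group.

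**Conclusion.** The conflict is real and confined to the definition and tables of post-treatment events. As written, SAP 5.8.1 starts these events at the earlier limit, while SAP 5.8 and the protocol keep the patient on treatment until the later one. On schedule, this gives 28 days of double classification after a stop at day 1 or week 8, 56 days after a missed week-8 infusion with SC dosing continued to week 12, and none after full dosing or a stop at week 4. The dose window allows up to 14 days in fully dosed patients.

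These figures assume that 5.8.1 is applied literally. The documents do not give the number of patients stopped at each dose or the number of events between the limits, so the effect on any table cannot be computed. The report's main safety tables, the special-interest tables and the efficacy analysis do not change. The wording should be corrected because the post-treatment AE and serious AE tables would otherwise depend on the programmer's choice of boundary, in a study where dosing was cut short.

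**What to change.** In SAP 5.8.1, define post-treatment AEs as AEs that developed or worsened during the post-treatment follow-up period of Section 5.8, that is, after the later of 28 days after the last SC dose and 56 days after the last IV dose. Retitle the two Post-Treatment TEAEs outputs as Post-Treatment AEs.

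The cost is one sentence and two table titles. No data collection, clinical rule or efficacy analysis changes, and 5.8.1 then agrees with SAP 5.8 and Protocol 9.5.3.1.
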